5.4.1.1 Heterogeneity of treatment effects (HTE)

N-of-1 trials may be more effective for some types of patients than for others. In addition, to checking interaction with baseline AFEQT, we will examine interactions of treatment with the potential between-patient modifiers listed in Table 2 in regression models as exploratory analyses. These will include medical history, demographics, medications, mood and sleep.

5.4.1.2 Missing Data

We will attempt to obtain a 10-week AFEQT value when a patient drops out of the study. When the primary 10-week endpoint is missing for a patient, we will use different approaches to estimate sensitivity of conclusions to the missing data assumption: 1) disregard the missing outcome and discard the patient from analysis; 2) multiple imputation; 3) assume no change from baseline to 10 weeks. The third analysis is likely to be conservative, but makes a fairly strong assumption about the missing not at random assumption (MNAR).

Other endpoints such as average frequency, severity, duration and number of safety events will be calculated based on the data reported. We will assume that days where no safety events or AF events are reported are event-free and so there will be no missing values for the other outcomes.

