Meta-Analysis of N-of-1 Trials: The collection of individual N-of-1 trials can be thought of as a set of studies whose results can be combined as in a meta-analysis. The data can be considered as a multilevel structure in which a set of patients is studied with each patient having a set of measurements. Standard multilevel mixed model methods will be used to estimate the average effect and variance within and across patients. Across patient values estimate the average effect in the population of patients studied, while the within-patient estimates describe an improved estimate of each patient's true effect assuming exchangeability across patients. We will fit these models using a Bayesian multilevel model with non-informative priors in order to obtain posterior distributions of the within and between effect sizes. We will then compare the multilevel patient estimates with those from the patient's data alone in order to determine how much the effects change and how much additional precision these estimates gain.

Analysis of Comparative Effectiveness: The experimental design is a simple two-arm randomized trial comparing N-of-1 vs. symptom surveillance. The primary outcome is the change in the AFEQT scale from baseline to 12 weeks. The mean change in each treatment group will be compared by a t-test. The average frequency and severity of AF episodes per week during the final month of each participant's enrollment will be the secondary

outcomes. Their group means will also be compared with a t-test. We will check for balance in covariates across the randomized groups and will adjust for any imbalances by including those covariates in regression analyses and reporting the adjusted treatment effect as a secondary analysis.

Missing Data: A major purpose of this aim is to determine the feasibility and usability of N-of-1 studies for actual application in clinical practice. Therefore, carefully documenting adherence and completion rates and predictors of each will be an important aspect of this study. Within the HeH study, we have found that >90 % of all AF HeH study participants complete all AF-related surveys, including the AFEQT. The primary analysis will be intent-to-treat which uses all participants as randomized. When no endpoint is available, we will assume no change. Further analyses will employ multiple imputation to fill in missing values, particularly in covariate-adjusted models ([name]-3).

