4.6 Data Sources

- **4.6.1**. **Case Report Forms**: Because the study is conducted remotely and via a mobile app, it will not employ formal case report forms. Instead, surveys will be delivered via the mobile app in two forms: 1. During initial on-boarding, patients will answer a series of surveys delivered in consecutive order. These surveys will remain on the app (and will be the first thing a patient sees when they interact with the app) until they are completed. 2. Short surveys will be delivered via push notifications from the app.
- **4.6.2 Eureka Technology Platform**: Individuals will enter data via the Eureka mobile app. As with the great majority of research in the Health eHeart Study that is obtained remotely and from patient self-entry, the study will rely on a framework of patient reported data. Patients who fail to complete surveys will be sent reminders via app-related push notifications or SMS text messages.

4.7 **Data Access and Reports** During the study, the Eureka data management team at the University of California, San Francisco will have access to the raw study data from all data sources. Standardized reports will be generated to allow the study team to monitor recruitment and retention, progression through the phases of the N-of-1 trial and/ or data tracking arm, completion of surveys, and responses to study activity notifications. These outputs will be visualized in real-time using the Eureka administrative portal and reports can be printed or provided as a PDF as needed. In coordination with the study statistician, the Eureka data management group will also prepare reports for the data safety and monitoring board (DSMB). These reports will include data on: accrual, data quality and completeness, study withdrawals, rates of completion of N-of-1 trials, and hospitalizations and emergency room visits.

At the conclusion of the study, the data coordinating center will work with the study biostatistician to prepare the analytic data files to be used in the final analysis. The study statistician will only be obtaining and using de-identified data for this project. Please see attached letter from Brown IRB regarding the non-human subjects waiver.

5. Analytic Plan

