5.4.3.3 Missing Data

Missing data in individual N-of-1 trials are likely going to be most pertinent to the daily measures of AF and duration and severity. We will treat days on which the patient makes no report as having no AF event. As with the analyses in Aim 1 with cases of missing outcome data, we will both ignore the missing values (assuming missing at random) and treat the missing values as latent parameters and estimate them as part of the Bayesian model assuming them to be missing at random. If we suspect that data are missing not at random (MNAR), we will construct MNAR models based on the appropriate missing data patterns to determine sensitivity of inferences to this assumption. If any data on effect modifiers are missing, we may also attempt multiple imputation, particularly if the number is large and the number of latent parameters to be estimated becomes too large.

6.Potential Impact:

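### Days without a report are analysed as event-free for the between-arm AF and safety outcomes, with no sensitivity analysis, although skipped days can be identified; AF frequency is the outcome most exposed

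*SAP*

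**What the plan says.** SAP 5.4.1.2 gives a missing 10-week AFEQT three approaches: discard, multiple imputation, and no change. For everything else it says "Other endpoints such as average frequency, severity, duration and number of safety events will be calculated based on the data reported", and then "We will assume that days where no safety events or AF events are reported are event-free and so there will be no missing values". No alternative follows.

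Skipped days are visible in the data. SAP Table 2 (section 4.1) records the daily AF event as Yes or No, and SAP 4.7 has reports on "completion of surveys, and responses to study activity notifications". Protocol 1.7.2 says that "carefully documenting adherence and completion rates and predictors of each will be an important aspect of this study" and that "Further analyses will employ multiple imputation to fill in missing values, particularly in covariate-adjusted models", but ties neither to the daily or safety outcomes.

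For the N-of-1 trials, SAP 5.4.3.3 states: "We will treat days on which the patient makes no report as having no AF event". It continues that "we will both ignore the missing values (assuming missing at random) and treat the missing values as latent parameters", and adds: "If we suspect that data are missing not at random (MNAR), we will construct MNAR models".

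SAP 5.4.1 compares weekly AF frequency, duration and severity in the final month of enrolment by t-test, and analyses each safety event as any versus none. SAP 4.3 averages duration and severity over AF episodes. SAP 4.2 scores an AF-free day as 0 for duration and 1 for severity. Table 2 codes an unanswered final-month duration or severity as 0, and schedules the safety questions at weeks 4 and 8.

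**The concern.** A day on which the participant answered No and a day on which the participant answered nothing carry different information, and the rule makes them equal. If one arm answers less often, its AF frequency falls for that reason alone, which can create a difference, hide one or enlarge one. Reducing AF frequency and severity is the stated objective (Protocol 1.2), so these secondary results will be read closely. The multiple imputation in the protocol does not help, because under the SAP rule nothing is left to impute.

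Two related gaps follow from the same section. In the N-of-1 trials the rule comes before the methods meant to examine it. For safety, time after the last scheduled question is counted as free of events.

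**Working it through.** **Inputs.** From the documents: 239 per arm (SAP 5.2), t-test and 0.05 level (SAP 5.4.1), a final-month window taken as 28 days, a 10-week comparison, and safety questions at weeks 4 and 8. Assumed, because the documents do not give them: reporting rates, mean AF days (5.6, 2.8 or 1 per 28), between-patient spread (Beta with precision 4 or 1), and a two-sided test. AF days stand in for episodes, since the daily item is Yes/No. Each setting used 4,000 simulated trials. The plan states no figure on this point to reproduce.

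**1. Frequency, skipping unrelated to AF.** With daily AF probability p and reporting rate r, expected counted AF days are 28 × p × r, so

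apparent ratio = true ratio × (r1 / r2).

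With no true difference: 0.85/0.90 = 0.94; 0.80/0.90 = 0.89; 0.70/0.90 = 0.78.

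False positives under the SAP rule (%):

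| Mean AF days per 28 (precision) | 85 vs 90 | 80 vs 90 | 70 vs 90 |
|---|---|---|---|
| 5.6 (4) | 9.9 | 24.7 | 78.4 |
| 5.6 (1) | 7.6 | 14.1 | 46.2 |
| 2.8 (4) | 7.9 | 14.8 | 44.1 |
| 2.8 (1) | 5.6 | 9.3 | 22.9 |
| 1 (4) | 6.5 | 9.0 | 17.8 |
| 1 (1) | 5.0 | 5.7 | 11.3 |

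AF days per reported day give 4.3-5.6% throughout. A repeat run gave 5-10%, 6-26% and 11-81% for the three columns.

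**2. Frequency, true 25% reduction** (5.6 days per 28, precision 4; N-of-1 arm reporting 90%):

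| Control reporting | Apparent ratio | Power, SAP rule | Power, per reported day |
|---|---|---|---|
| 90% | 0.75 | 88.2% | 88.4% |
| 85% | 0.75 × 0.90/0.85 = 0.79 | 70.4% | 88.5% |
| 80% | 0.75 × 0.90/0.80 = 0.84 | 46.4% | 89.0% |
| 70% | 0.75 × 0.90/0.70 = 0.96 | 6.2% | 88.7% |

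With control at 90% and the N-of-1 arm at 85, 80 or 70%, the ratio is 0.71, 0.67 or 0.58, so the benefit is exaggerated.

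**3. Other skipping patterns, no true difference.** If only AF-free days are skipped, the SAP rule stays at 4.5-5.6%, while the per-reported-day analysis gives 5-13% at 80 versus 90 and 6-43% at 70 versus 90 (up to 45% in the repeat run). If AF days are reported 70 versus 90% and AF-free days 90% in both arms, the SAP rule gives 11-80% and the per-reported-day analysis 7-43%.

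**4. Duration and severity.** SAP 4.3 averages over episodes, so a skipped day does not enter. With skipping unrelated to AF, false positives stay at 4-6% even at 70 versus 90. Table 2, by contrast, describes a total duration; if that is the version analysed, it shrinks with reporting as frequency does. The per-episode averages are undefined for a participant with no reported episode. At 90% reporting that is 17-87% of participants under the assumed AF rates. The daily codes in SAP 4.2 (0 and 1) hint at a rule but are not reconciled with SAP 4.3.

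**5. N-of-1 trials.** Once a no-report day is set to no AF, the self-reported AF event has no missing value, so ignoring missing values, latent parameters and MNAR models have nothing to act on for that outcome. They can still act on days without an ECG (ECG-flagged AF is also an N-of-1 outcome in Table 2) and on unanswered duration or severity.

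**6. Safety.** The last question at week 8 leaves 2 of 10 weeks (20%) unasked for participants who stop at week 10. At constant risk a true 5% incidence is recorded as 1 − (1 − 0.05)^(8/10) = 4.0%.

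**The case against.** The strongest reply is that the SAP rule may be the right one. Participants have symptomatic AF and are told to record an ECG when they feel an episode, so silence may mostly mean no AF. Step 3 shows that the planned analysis is then valid and the per-reported-day analysis is the biased one. This stands: a reader might infer that the rule should be replaced, but no document shows which pattern is nearer the truth, so only adding a second analysis is supported.

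A large reporting gap is also not established. In the last four weeks of a first trial the trigger reminders and trigger tracking have stopped (Protocol 1.5), so daily tasks are similar in the two arms, and the 70 versus 90 column is an extreme. On the other side, the arms reach that window after different routines, and Protocol 1.7.1 plans 600 starters for 478 completers (1 − 478/600 = 20.3% non-completion). Unequal reporting is possible; its size is unknown.

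Three further inferences go too far. Scoring early dropouts as AF-free fits only those who stay enrolled and silent, because a window defined as the final month of enrolment moves earlier for someone who formally withdraws. The code 0 for an unanswered duration equals the value for an AF-free day, but duration is asked only after a Yes, so the raw data can separate the two. And the safety wording elsewhere is monthly (Protocol 1.8.1, SAP 4.4), so participants who continue may be asked later; those who stop at week 10 have no listed question.

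**Conclusion.** The concern holds for AF frequency, and for total duration if the Table 2 version is used. SAP 5.4.1.2 fixes one untestable assumption for unreported days and plans no check of it, although skipped days can be identified. With skipping unrelated to AF, a 5-point reporting gap does little, a 10-point gap can take false positives from 5% to as much as about 26%, and a 20-point gap to about 80% at the highest AF rate with the smaller spread. All reporting and AF rates are assumptions, and the direction is unknown.

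The documents do not support a wider reading. The primary AFEQT analysis has its own three approaches and is untouched. The per-episode duration and severity averages are not biased by this mechanism; their problem is the missing rule for participants with no episodes. The methods in SAP 5.4.3.3 are not wholly idle; they are blocked for the self-reported AF event only. The week 9-10 gap understates incidence in both arms alike and creates no arm difference. This should be corrected before the secondary outcomes are analysed.

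**What to change.** 1. In SAP 5.4.1.2, add an analysis of AF days per reported day over a fixed window, weeks 7-10 from the start of tracking, with imputation for participants who have no report in it. A fixed window is needed because the final month of enrolment shifts with withdrawal and with later trigger tests. Present it beside the analysis that counts no report as no AF, with response rates by arm, and interpret frequency in the light of both. Each is biased under some skipping pattern, and neither protects against skipping on AF days, so agreement should not be required.
2. In SAP 5.4.3.3, confine the rule that no report means no AF to one of the analyses, so that the missing-data methods already planned can be run on the AF event.
3. Give unanswered duration and severity a missing code distinct from any real value, and reconcile SAP 4.2 with 4.3 for participants with no episodes.
4. Add the existing safety prompt at week 10 with the AFEQT in both arms, or limit the safety analysis to the queried time.

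The cost is SAP wording, a coding change, a little more analysis and one prompt at an existing contact. At equal 90% reporting the added analysis loses no power (88.4% against 88.2%). The simulation left out participants with no reports rather than imputing them, so the imputation step itself has not been tested.

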1.7 Statistical Plan

1.7.1 Sample Size Determination

We conservatively estimate that the available pool will include 10,000 engaged individuals meeting the inclusion and exclusion criteria. Given that we estimate that 478 participants will be needed, we need to consent only 5% of eligible patients. Strategies to overcome barriers to enrollment include continuing aggressive efforts to recruit large numbers of HeH participants (in collaboration with the HeH Alliance and partners such as the AHA) and ongoing messaging from the CEO and other leadership encouraging enrollment to StopAfib.org participants and visitors (Std PC-2). In order to achieve at least 478 patients that complete the 6 month study, we will aim to initiate at least 600 patients.

Sample Size & Power Calculations: As those with at least moderate AF severity have an AFEQT score of 58 ± 1958 and the most modest of therapies typically improves this score by a mean of 5-10, we have powered this study conservatively to detect an improvement of 5 points in the AFEQT. We estimate 239 patients in each group would provide 80% power to detect this small, yet still clinically meaningful difference. Given the enthusiasm of >1000 AF patients already engaged by the investigators, we believe enrollment will not pose a challenge.

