Hospitalization	Patient report	1=Yes 2=No 3=Don't know If yes, date and hospital location	Monthly; actual hospitalizations will be categorized by day reported at 4 and 8 weeks.	Eureka app
Hospitalization related to atrial fibrillation	Patient report	1=Yes 2=No 3=Don't know	Monthly (queried only if hospitalization=Yes for that month)	Eureka app

			Reported at 4 &8	
			weeks.	
Cerebrovascular accident	Patient report	1=Yes 2=No 3=Don't know If yes, date and location diagnosis	Monthly; reported at 4 &8 weeks.	Eureka app
Myocardial infarction	Patient report	made 1=Yes 2=No 3=Don't know If yes, date and location diagnosis made	Monthly; reported at 4 &8 weeks.	Eureka app
Heart failure	Patient report	1=Yes 2=No 3=Don't know If yes, date and location diagnosis made	Monthly; reported at 4 &8 weeks.	Eureka app
MODIFIERS	_			
Age	Patient report	Continuous	Baseline only	Eureka app
Gender Identity	Patient report	1=Woman 2=Man 3=Transgender Woman 4=Transgender Man 5=Genderqueer 6=Another gender identity 7=Decline to state	Baseline only	Eureka app
Sex	Patient report	1=Male 2=Female 3=Prefer not to state	Baseline only	Eureka app
Race	Patient report	1=Black 2=White 3=Asian 4=Native Hawaiian or Pacific Islander 5=American Indian or Alaska Native 6=Some other race 7=Don't know	Baseline only	Eureka app

		8=Prefer not to		
		state		
Hispanic	Patient report	1=Not Hispanic 2=Yes: Mexican, Mexican American or Chicano 3=Yes: Puerto Rican 4=Yes: Cuban 5=Yes: Cuban 5=Yes: Mixed Hispanic, Latino or Spanish Origin 6=Yes: Other Hispanic, Latino, or Spanish Origin 7=Don't know 8=Prefer not to state	Baseline Only	Eureka app
Education level	Patient report	1=No formal schooling 2=Some school, but did not graduate high school 3=High school diploma or equivalent 4=Associate degree 5=Some college 6=Bachelor's degree 7=Master's degree 8=Doctorate 9=Professional doctorate 10=Other 11=Don't know 12=Prefer not to state	Baseline Only	Eureka app
Household income	Patient report	1= Under \$10,000 2= \$10,000 to under \$20,000 3= \$20,000 to under \$30,000	Baseline Only	Eureka App

		4=\$30,000 to		
		under \$40,000		
		5= \$40,000 to		
		under \$50,000		
		6= \$50,000 to		
		under \$75,000		
		7= \$75,000 to		
		under \$100,000		
		8= \$100,000 to		
		under \$150,000		
		9= More than		
		\$150,000		
		10= Don't know		
		11= Prefer not to		
		state		
Household size	Patient report	Integer 0-20	Baseline Only	Eureka app
Hoight	Dationt report	Integer 1 10 ft	Pacolino Only	Euroka ann

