4.4. Safety Endpoints

- 1. **Hospitalization** Days on which any hospitalization occurs together with date and hospital location. This will be recorded from the Eureka app and will be reported monthly by the patient.
- 2. **Hospitalization related to atrial fibrillation** Days on which a hospitalization related to atrial fibrillation occurs together with date and hospital location. This will be recorded from the Eureka app and will be reported monthly by the patient.
- 3. **Emergency department visit** Days on which any emergency department visit occurs together with date and hospital location. This will be recorded from the Eureka app and will be reported monthly by the patient.
- 4. **Cerebrovascular accident** Days on which any cerebrovascular accident occurs together with date and hospital location. This will be recorded from the Eureka app and will be reported monthly by the patient.
- 5. **Myocardial infarction** Days on which a myocardial infarction occurs together with date and hospital location. This will be recorded from the Eureka app and will be reported monthly by the patient.
- 6. **Heart failure** Days on which heart failure occurs together with date and hospital location. This will be recorded from the Eureka app and will be reported monthly by the patient using language from previous HeH surveys.

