5.4 Analysis

5.4.1 Comparison of N-of-1 to data tracking

The experimental design for Aim 2 is a two-arm randomized trial comparing N-of-1 vs. symptom surveillance. The primary endpoint is AF severity via the AFEQT from baseline to 10 weeks. Differences between treatment groups will be compared using analysis of covariance with the 10 week measurement as the outcome and the baseline measurement as covariate. We will also test for an interaction between treatment and baseline AFEQT in order to measure possible treatment effect heterogeneity. The average frequency, duration and severity of AF episodes per week during the final month of each patient's enrollment will be secondary outcomes. Their group means will be compared with a t-test. Additional secondary outcomes will include safety events: hospitalizations, emergency room visits, stroke, myocardial infarctions and heart failure. The main analysis will treat each of these as a binary outcome indicating the incidence of any event. We will also investigate models for multiple Version 1.0 5/12/17

events per person if these are common. We will check for balance in covariates across the randomized groups and will adjust for any imbalances by including those covariates in regression analyses and reporting the adjusted treatment effect as a secondary analysis. The null hypothesis of no difference will be tested at a significance level of 0.05.

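### The SAP scores silence on safety prompts as no event and recognises no missing safety values; the last scheduled safety report is week 8 of 10, and death is not a listed endpoint

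*SAP*

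**What the plan says.** SAP section 4.4 lists six safety endpoints: hospitalization, AF-related hospitalization, emergency department visit, cerebrovascular accident, myocardial infarction and heart failure. The source is the same for each: "This will be recorded from the Eureka app and will be reported monthly by the patient". Table 2 (SAP section 4.1) adds AF-related emergency room visits and codes the items Yes, No or Don't know. It times all of them at weeks 4 and 8; the stroke, infarction and heart failure rows read "Monthly; reported at 4 &8 weeks".

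SAP section 5.4.1 makes these events additional secondary outcomes in the randomised comparison: "The main analysis will treat each of these as a binary outcome indicating the incidence of any event". SAP section 5.4.1.2 then sets the missing-data rule, which assumes that "days where no safety events or AF events are reported are event-free and so there will be no missing values for the other outcomes".

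The same section treats the AFEQT differently. It promises that "We will attempt to obtain a 10-week AFEQT value when a patient drops out of the study" and gives three analyses for a value that is still missing.

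Death is not in SAP section 4.4, Table 2, SAP section 5.4.1 or Protocol section 1.8.1. Protocol section 1.9.1 seeks vital status, but only for participants who revoke authorisation.

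**The concern.** The rule merges two different states: a participant who answered No, and one who did not answer. The data can tell them apart, because No has its own code. Once they are merged, the binary variable is defined for everyone and non-response drops out of the safety comparison.

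Silence may also carry information. Someone who dies or has a disabling stroke cannot complete the next monthly prompt, and under the rule is event-free unless an earlier event was reported. Events are then undercounted. If silence is more common in one arm, that arm looks safer. What is at stake is whether a statement that few or no serious events occurred can be read against the number of people who were actually asked and answered.

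**Working it through.** The plan gives no figure for safety non-response, so there is nothing to reproduce. The check sets the rules side by side and then shows the size under stated assumptions.

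**Path of a silent participant.** A prompt goes unanswered at weeks 4 and 8. No event is on record, so section 5.4.1.2 scores the days event-free. Section 5.4.1 then records no event, and the participant stays in the denominator. The models for data missing not at random in SAP section 5.4.3.3 concern the daily AF measures within N-of-1 trials and do not reach this comparison.

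**Uncovered time.** Randomised follow-up is 10 weeks (SAP Executive Summary and section 4.2) and the last scheduled safety report is at week 8: (10 - 8)/10 = 20%, for participants who stop at week 10.

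**Guides to non-response.** There are two, and neither measures answers to the safety prompts.
- Protocol section 1.7.1: "In order to achieve at least 478 patients that complete the 6 month study, we will aim to initiate at least 600 patients". The allowance is 600 - 478 = 122, and 122/600 = 20.3%, but over six months.
- Protocol section 1.7.2: more than 90% "of all AF HeH study participants complete all AF-related surveys", in the parent cohort.

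**Bound when no event is reported.** The one-sided 95% upper bound is 1 - 0.05^(1/n).
- All scored event-free, n = 600/2 = 300 per arm: 0.99%.
- Only reporters counted, n = 0.90 x 300 = 270 per arm (assuming 90% answer the safety prompts): 1.10%.

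The difference is about 0.1 percentage point.

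**Undercount (assumed values).** Let p be the true 10-week any-event risk with constant hazard, and q the share who answer no prompt. Suppose nothing after week 8 is captured. The observed risk is (1 - q) x [1 - (1 - p)^0.8]. For p from 2% to 10%, the share of participants with an event who are missed is:

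| q | Missed |
|---|---|
| 0 | 19-20% |
| 10% | 27-28% |
| 20% | 35-36% |

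**Shift between arms (assumed values).** With equal true risk, the observed risk ratio is (1 - q_high)/(1 - q_low).
- 5% against 15%: 0.85/0.95 = 0.89.
- 10% against 20%: 0.80/0.90 = 0.89.
- Equal q in both arms: 1, so no shift.

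**Against chance.** Take 300 per arm and an assumed 2% risk, so 6 events per arm. The standard error of the log risk ratio is sqrt(2 x (1/6 - 1/300)) = 0.572. The 95% interval around a ratio of 1 is exp(±1.96 x 0.572), or 0.33 to 3.07. A shift to 0.89 is small beside that.

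**The case against.** The strongest reply is that little turns on this. Safety events are additional secondary outcomes in a trial described as low risk, and the illustrated shift lies well inside chance variation. That stands, and it limits the point to counting and reporting.

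Safeguards exist. "Patients who fail to complete surveys will be sent reminders via app-related push notifications or SMS text messages" (SAP section 4.6.2). DSMB reports cover data completeness and withdrawals (SAP section 4.7), and Protocol section 1.7.2 undertakes to document adherence and completion. The reports are retrospective and dated, so a patient who is hospitalised and recovers can report it at the next prompt. These measures reduce or describe silence, but none changes how it is scored.

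Four stronger readings are tempting and are not supported.
- A reader might infer that non-response is concealed. The SAP states its assumption openly and completion rates are to be documented, although completion of the safety items by arm is not promised.
- A reader might take the 478 as the number with safety reports. They are planned completers of a six-month study, and someone who leaves in month 4 could have answered both prompts. SAP section 2 also plans to recruit 478, not 600.
- A reader might infer that the N-of-1 arm will look safer because it carries more tasks. No dropout by arm is given. The week 9-10 gap is scheduled identically in both arms and does not by itself favour either.
- A reader might infer that no deaths could come to light. Protocol section 1.8.1 says monthly without a stated end, so those who continue may get later prompts. The DSMB charter lets its first meeting discuss which key safety variables to review. The consent pages are not in the public text.

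**Conclusion.** The concern holds as a fault in a stated rule. Non-report is scored as no event, no missing values are recognised, the schedule stops two weeks short of the randomised period, and death is not a listed endpoint in the visible text. The result is that events can be undercounted and the safety comparison does not show how many participants were not assessed.

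The size cannot be computed from the documents, which give neither event rates nor prompt non-response. On the assumptions shown, the zero-event bound moves from 0.99% to about 1.10%, and a ten-point difference in silence between arms gives a risk ratio near 0.89. The undercount percentages rest on constant hazard, complete silence among non-reporters and no later prompt. None of this suggests a wrong test result, and the AFEQT analysis is untouched. The change is worth making because it is cheap and the data already distinguish No from silence.

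**What to change.** 1. In SAP section 5.4.1.2, treat a period with no safety report as unknown. Report the number unknown, and the number answering Don't know, by arm. Show the binary comparison among those with reports beside the planned one.
2. Add the existing safety items to the week-10 AFEQT survey, which closes the gap after week 8, and to the dropout contact already planned for the AFEQT.
3. List death in SAP section 4.4, recorded when it is learned of through that contact. This will not find every death.

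A sensitivity analysis over a range of assumed risks for the unknowns is optional.

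The cost is SAP wording, a few more questions at two contacts already planned, and some unknown entries in the safety results. No new visit or larger sample is needed.
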